A. Study Type and Design: This is a crossover study with both PwMS and age and sex-matched neurotypical controls. 30 PwMS and 20 neurotypical controls be randomized into two groups and will participate in two split-belt treadmill training sessions while outfitted with cortical fNIRS and TENS devices on their bilateral tibialis anterior and rectus femoris. The first group will complete split-belt treadmill training with TENS OFF during the first visit and TENS ON during the second visit. The second group will complete split-belt treadmill training with TENS ON during the first visit and TENS OFF during the second visit to control for a learning effect. In between visits there will be a 4-week washout period. Participants will receive TENS only during the 10-minute split-belt adaptation period of the paradigm. During all other periods the TENS will be OFF.

B. Sample size, statistical methods, and power calculation

1. Total number of subjects who will be approached (including screen fails, controls and subject withdrawals) to reach enrollment numbers for the lifetime of the study for this investigator's site: 60
2. Total number of subjects to be enrolled at this site: 50

INSTITUTIONAL REVIEW BOARD NON-EXEMPT PROTOCOL TEMPLATE

3. Brief Description/justification for the proposed sample size in *lay terms*: From our preliminary data we computed a large effect size of 1.01 for change in brain activity in the SMA from baseline walking to split-belt treadmill training. According to our power analysis, to maintain an alpha of 0.05 and a power of 0.8, at least 10 participants per group are needed to detect significant changes in brain activity.
4. Simple randomization will occur (TENS first or TENS second) for both groups (PwMS and neurotypical controls).
5. No masking will occur in this study.

C. Subject Criteria (See Vulnerable Populations appendix 1, if applicable): PwMS and neurotypical controls from ages 18-86. All races and genders are included.

1. Inclusion criteria:

- A diagnosis of relapsing remitting multiple sclerosis OR a neurotypical adult (ages 18-86)
- Not experiencing an active relapse
- Able to stand and walk without an assistive device
- Able to walk for three tenths of a mile without stopping to rest
- MS participants must have a neurologist confirmed diagnosis of relapsing-remitting MS.
- MS participants must be independently ambulatory in the community, expanded disability status scale (EDSS) score < 5 (clinical measure of MS severity).

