- **TENS Protocol.** 30 PwMS and 30 age- and sex- matched controls will be randomized into two groups and complete two split-belt treadmill training sessions identical to Aim 1, while outfitted with cortical fNIRS and TENS devices on their bilateral tibialis anterior and rectus femoris. The first group will complete split-belt treadmill training with TENS OFF during the first visit (these are the participants in Aim 1) and TENS ON during the second visit. The second group will complete split-belt treadmill training with TENS ON during the first visit and TENS OFF during the second visit to control for a learning effect. In between visits there will be a 4-week washout period (Figure 3). Participants will receive TENS only during the 10-minute split-belt adaptation period of the paradigm. During all other periods the TENS will be OFF. We will use an FDA-approved clinical TENS device, the LG-TECELITE Therapy System (LGMedSupply, Cherry Hill, NJ). Stimulation will consist of bursting biphasic pulses delivered with electrode pairs (2 in. \times 4 in. pads) placed on the skin over the

INSTITUTIONAL REVIEW BOARD NON-EXEMPT PROTOCOL TEMPLATE

stimulated muscles. The stimulus frequency will be set at 5 Hz with a seven pulses of 0.15 ms based on recent evidence suggesting that bursting TENS is most effective for improving walking performance and limits nerve accommodation to the stimulation. The amplitude of the TENS stimulation will be individualized for each participant in accordance with their specific motor threshold. The TENS amplitude will be slowly increased at 1 mA increments on each individual muscle until non-voluntary muscle contractions can be seen or felt by the investigator, then the amplitude will be set to 2 mA below the motor threshold for each muscle and limb during the split-belt adaptation period. Additionally, we are choosing to outfit TENS on the tibialis anterior and rectus femoris due to previous studies successfully improving gait performance in PwMS using these stimulation locations (Figure 3).

[figure not shown]

Figure 3. (Left) Study design schematic including randomization and TENS condition at each visit. (Right) Example of TENS electrode placement on the bilateral tibialis anterior and rectus femoris.

- **Clinical Assessments**

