During the first visit participants will complete clinical testing to gain a more holistic view of their symptoms. The first test a vibration sensory threshold assessment on the left and right hallux. This threshold testing involves the use of Rydel-Seiffer vibrating tuning fork. This tuning forks provides a visual measurement of vibration, allowing for a quantifiable measurement of vibration perception across participants. It has also been shown in recent work that lower limb sensory perception is associated with split-belt treadmill adaptation. Additionally, we will include the modified Clinical Test of Sensory Interaction for Balance (mCTSIB) using the BTrackS system. This is a very commonly used clinical assessment for balance that is noninvasive and easy to implement. This test can distinguish the function of different domains of balance individually, including vision, proprioception, and vestibular function. An assessment of each balance domain will additionally allow us to better quantify the factors that contribute to successful adaptation on the split-belt treadmill. Both of these assessments will be performed by a postdoctoral fellow in our lab, [name], who is a board-certified doctor of physical therapy (DPT) and will take around five minutes in total.

- **Photo/Video Use**

INSTITUTIONAL REVIEW BOARD NON-EXEMPT PROTOCOL TEMPLATE

Additionally, photos or videos may be taken for gait analysis purposes, and qualitative assessment of gait adaptation. Participants may choose to opt in or opt out of this via the informed consent form.

3. All Procedures are for research purposes only and are not a part of standard therapy.
4. No biospecimens are used in this study.

E. Costs to Subjects: The only cost to participants is transportation to our lab and their time (approximately 4-6 hours over two sessions).

F. Payment, including a prorated plan for payment: Participants will be compensated via cash. Participants will receive a total of \$100.00 for completing the study. If a participant only finishes the first day of the study that participant will receive \$50.00. Upon completion of the second day that participant will receive an additional \$50.00. If a participant drops out or withdraws from the study partway through a session that participant will still be compensated \$50.00.

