G. Research-related injury: The Colorado Governmental Immunity Act determines and will limit Colorado State University's legal responsibility if an injury happens because of this study. Claims against the University must be filed within 180 days of the injury.

H. Risk/benefit assessment: Greater than minimal risk

1. Physical risk: Yes.
 - i. Musculoskeletal injury. There is a low risk of joint, tendon, or muscle pain, inflammation, or swelling during or after a testing session of your gait, and balance. This risk is reduced through the use of well-trained assistants and also by the mild nature of the gait and balance testing.
 - ii. Falls. The walking tasks may cause participants to lose their balance and fall. However, during the overground walking trials the research team is trained to walk alongside participants at all times; if a participant happens to lose their balance, research staff will be there to assist and prevent a fall. For the treadmill walking trials, participants will be wearing a harness attached to a secure beam to ensure safety and security while walking. All safety measures will be taken to ensure a secure and comfortable environment. Participants will be allowed to take a break from walking tasks whenever necessary. It is not likely that a participant will fall.
 - iii. Headache. Although rare, a potential side effect of our brain measurement is headache due to pressure on the scalp. However, we have many adjustments available in our cap to make the participant as comfortable as possible and mitigate this risk.
 - iv. Skin Irritation. The electrical impulses that a TENS unit produces may cause a buzzing, tingling, or prickling sensation, which some people may find uncomfortable. Some people may be allergic to the adhesive pads. In rare cases, patients have reported burns at the sites where the electrodes are placed. However, we use a very mild level of stimulation which greatly reduces this discomfort. A TENS unit consists of a battery-powered device that delivers electrical impulses through electrodes (or sticky pads) placed on the surface of your skin. Overall, for the vast majority of people, TENS is believed to be safe and well-tolerated with little to no side effects. However,

INSTITUTIONAL REVIEW BOARD NON-EXEMPT PROTOCOL TEMPLATE

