 - a. Persons/groups who will review the data (study team; independent safety monitor, data monitoring committee or formal DSMB). This study is a registered clinical trial on clinicaltrials.gov (NCT05878873) where [name] is the lead investigator and will be responsible for trial monitoring. Confidentiality will be strictly maintained to minimize psychological and economical risks. Participant identities will be kept confidential via participant identification numbers (i.e. SBNT_000). The computer

INSTITUTIONAL REVIEW BOARD NON-EXEMPT PROTOCOL TEMPLATE

that will store the project database will be protected by current network security. An institutional computer account and password will be required to access the computer storing the recruitment database and the REDCap database will be password protected, and only project personnel approved by the PI will be given access. Only those individuals listed on the IRB consent form and within the Kuali IRB protocol will have access to the data.

- b. Data/events that will be reviewed: Objective, de-identified data will be reviewed in a rolling fashion throughout the course of this project to allow for dissemination of preliminary results and for the use of preparing future grants based upon results. Any adverse events that occur will be documented, reported and reviewed immediately.
- c. Frequency of review: Data will be reviewed monthly by our team.
- d. Types of analyses to be performed: Analyses include objective outcomes from the split belt treadmill training protocol. This includes gait kinematics and kinetics, as well as cortical activation as assessed by fNIRS data.
- e. Safety-related triggers that would cause the PI to alter the study/remove a participant: If an individual was unable to safely ambulate either on their own within the hallway, or on our treadmill in a safe and efficacious manner, participation would be halted immediately. Triggers that would identify an individual as a potential risk include repeated stumbling, tripping, or falls where our body weight support harness catches the individual.

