2. Describe how adverse events (anticipated and unanticipated) and unanticipated problems will be ascertained and handled. Explain exactly which type of problems will be considered serious and reported to the IRB. The reporting timeframe should also be detailed. The primary adverse event that could result from this protocol is an unintended fall by a participant. To mitigate any risks that would occur as a result of a fall we implement a number of safety measures including the use of a "gait belt" while walking overground and a body weight support harness while walking on our treadmill. These are standard of care practices and the PI of this project has conducted similar mobility-based research for nearly two decades and has yet to report an adverse event as a result of an accidental fall. If an individual were to fall during this project, we would immediately contact the medical director of the HPCRL, [name] for acute assessment. Following this, we would report to the IRB within 2 business days, as we believe any unintentional fall is an adverse event and requires reporting.
3. Explain exactly what will happen if a patient experiences an adverse event or other problem (for example, will discontinue study participation). As described above, immediate attention would be provided by our in-house physician and medical director, [name] and further steps will be conducted under his advisement. If an individual were to experience an accidental fall, we would discontinue study participation at that point.

IV. Data Collection and Protection

A. Data Management and Security:

1. All data collected, including identifiable information or personal health information will be stored either electronically on secured Colorado State University server or through a REDCap database with access restricted to study personnel. Any data not in electronic form

INSTITUTIONAL REVIEW BOARD NON-EXEMPT PROTOCOL TEMPLATE

will be stored in a locked file cabinet with access limited to study personnel. The Sensorimotor Neuroimaging Laboratory is located in Moby room 154 within the Department of Health and Exercise Science. All hard copy data will be stored in the Sensorimotor Neuroimaging Laboratory, with access being restricted to authorized key holders and key study personnel.

2. [name], [name], and [name] will have access to the study data.

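### Adverse-event ascertainment is described for falls only: no skin check, symptom question or contact is scheduled after either session, so the other named risks are captured only if noticed or volunteered

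*Combined protocol and SAP*

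**What the plan says.** Section III.H.1 lists four physical risks.

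- **Musculoskeletal (III.H.1.i):** "There is a low risk of joint, tendon, or muscle pain, inflammation, or swelling during or after a testing session". The sentence goes on to tie this to gait and balance testing.
- **Falls (III.H.1.ii).**
- **Headache (III.H.1.iii):** from pressure of the fNIRS cap.
- **Skin (III.H.1.iv):** "Some people may be allergic to the adhesive pads", and "In rare cases, patients have reported burns at the sites where the electrodes are placed".

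The template heading of III.N.2 asks how anticipated and unanticipated events will be ascertained and handled. The reply begins "The primary adverse event that could result from this protocol is an unintended fall by a participant" and stays with falls: preventive equipment, assessment by the medical director, and a report to the IRB within 2 business days. III.N.3 adds that the in-house physician would attend to an event.

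III.N.1.b commits the team to recording, reporting and reviewing without delay any adverse events that occur. For the monthly review, III.N.1.d states "Analyses include objective outcomes from the split belt treadmill training protocol" and specifies gait and fNIRS measures. The SAP (V.C) covers adaptation rate, adaptation savings and HbO beta, with no adverse-event summary.

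Section III.E puts participation at "approximately 4-6 hours over two sessions". The visits are 4 weeks apart (II.A).

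**The concern.** A safety plan has to say how events will be found as well as what happens once they are known. Here the second part is written in general terms and the first only for falls, which staff see as they happen. Pad reactions, burns under an electrode, cap headache and next-day soreness can all go unrecorded unless someone looks or asks, and one of these risks is described by the protocol itself as possible after the session.

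Section III.H.5 presents the study as informing whether TENS has potential as a rehabilitation strategy. If few or no events are recorded, readers may take that as evidence of tolerability when it partly reflects that no one was asked. The adaptation and fNIRS analyses are not affected.

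**Working it through.** The plan gives no figure on this point to reproduce. The check sets each named risk against the text that would detect it.

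| Risk in III.H.1 | Preventive measure stated | Method of finding it during the session | Method of finding it after the session |
|---|---|---|---|
| Musculoskeletal pain, inflammation, swelling | Trained assistants, mild testing | None stated | None stated |
| Falls | Staff alongside, gait belt, harness | Direct observation; III.N.1.e triggers | None stated |
| Headache | Cap adjustment | None stated | None stated |
| Pad allergy, electrode burns | Mild stimulation | None stated | None stated |

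Three of the four rows have no detection method at all. The preventive measures may lower the risk, but they do not record an event that happens anyway.

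Next, every other place where a check might be written:

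1. **III.B (screening).** REDCap surveys by private email, before testing begins. None is planned afterwards.
2. **III.D.2 (clinical assessments).** Vibration threshold and balance testing at the first visit. These are not symptom questions.
3. **III.D.2 (split-belt paradigm).** A 10-minute deadaptation walk follows the adaptation period in the same visit. Staff are present and might notice a problem, but no inspection or question is specified.
4. **Visit 2.** The participant returns about 4 weeks later. No question about events since visit 1 is written.
5. **III.N.1.b.** Governs events that have become known. It gives no method or time window for learning of them.
6. **III.N.1.e.** The triggers concern safe ambulation only.
7. **V.A.** The only later contact is a one-way summary of group results.

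Extent of the gap, by arithmetic:

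- II.B.2 enrols 50, so 50 × 2 = 100 sessions, of which 50 are TENS ON and 50 TENS OFF.
- The TENS Protocol text in III.D.2 gives 30 + 30 = 60 participants, so 60 × 2 = 120 sessions. The two totals need reconciling, but the conclusion is the same under either.
- Sessions with a scheduled post-session check: 0 of 100 (or 0 of 120), whichever the TENS state.

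The number of events missed cannot be calculated, because the documents give no event rates and no expected rate of volunteered reports.

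**The case against.** The best defence is that III.N.1.b already promises prompt recording and review of any adverse event and does not limit this to events seen by staff. III.N.3 also brings in the physician. Exposure is modest: one 10-minute period, set 2 mA below motor threshold. Instructions to participants on reporting problems would normally sit in the consent material, which is not part of the text available here.

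Much of this stands. Handling of known events is covered, and it cannot be said that participants have no route for reporting a later problem. What remains is that the protocol body solicits nothing, so capture depends on volunteering or on chance observation.

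Three stronger readings are tempting, and the documents do not support them.

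- **Harm capture depends on sequence.** One group has "The first group will complete split-belt treadmill training with TENS OFF during the first visit and TENS ON during the second visit", so its TENS session is its last, whereas the other returns after TENS. A reader might infer a biased ON/OFF safety comparison. But the only risk described as arising after a session is attached to gait and balance testing, which occurs at both visits in both sequences. No late onset is stated for burns or pad allergy. With balanced sequences, 25 of 50 ON sessions and 25 of 50 OFF sessions precede another visit, so neither condition is favoured. Balance is itself an assumption: II.B.4 says simple randomization and V.C says counterbalanced.
- **No contact after stimulation in the TENS-second group.** The 10-minute deadaptation walk follows stimulation in the same visit, in both sequences.
- **Half the TENS exposures are observable for delayed harm.** One could compute zero-event upper bounds of 1 − 0.05^(1/25) = 11.3% against 1 − 0.05^(1/50) = 5.8%. The arithmetic is right, but the contrast counts visit 2 as observation when no question is planned there. If only solicited events count, the written plan observes none; if volunteered reports count, TENS-second participants are not excluded.

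**Conclusion.** The point holds as an omission in the safety plan. Falls are covered while the session lasts. The other three physical risk items in III.H.1 have no stated means of ascertainment during or after either session, so events of those kinds will be under-counted in both TENS conditions. The size of the under-count is unknown.

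The conclusion rests on the protocol body and SAP alone and assumes that no solicited check appears in material not shown. It does not imply a biased ON/OFF comparison, and it does not touch the adaptation or cortical-activation analyses. It should be corrected because the study is rated above minimal risk, the protocol names these risks itself, and the remedy is cheap.

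**What to change.** In III.N.2, add the same solicited check after both visits, whatever the TENS state:

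1. When the equipment is removed, look at the electrode and cap sites and record the finding, including when nothing is seen.
2. Send a short REDCap survey at one fixed interval after each visit, asking about skin, pain or swelling, headache and falls. The private email route in III.B is already in use.
3. Record TENS state and group (PwMS or control) with each event.
4. In III.N.1.d and V.C, add a tabulation of adverse events by TENS ON/OFF and group, for the monthly review and the final report. Give the number of completed checks as the denominator, so that an absence of events can be told apart from an absence of replies.

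The cost is one REDCap form, about a minute per session, a small burden on participants and more minor events recorded. No stimulation setting, visit schedule or discontinuation rule changes.

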- Participants must be 18-85 years of age at the time of participation in the study.
- Participants must be able to stand/walk on a firm surface for least 30 minutes.
- Participants must be able to stand from a seated position on their own volition.

2. Exclusion criteria:

- Unable to walk for 500 meters without assistance
- Musculoskeletal injury in past 6 months
- Lower extremity surgery in past 6 months
- Unable to abstain from medications that impair balance
- Currently pregnant
- History of traumatic brain injury
- History of vestibular disease
- History of any other balance impairment unrelated to multiple sclerosis
- MS participants must not have primary progressive MS
- MS participants must not have on-going MS relapse
- MS participants must not have other neurologic conditions besides MS, and concurrent conditions affecting ability to comply with the study procedures including musculoskeletal injury
- MS participants must not have excessive fatigue to the extent that participants can not complete all testing required.
- Participants must not have significant vision impairment

3. Withdrawal/Termination criteria: Participants will be withdrawn if they are upon baseline walking assessment the researcher determines that they do not have enough mobility to complete the split-belt treadmill training paradigm.

INSTITUTIONAL REVIEW BOARD NON-EXEMPT PROTOCOL TEMPLATE

4. Participants are allowed to be concurrently enrolled in another research study, unless this study causes them to fall within the exclusion criteria.

III. Subject Participation

A. Recruitment:

1. Subjects will be recruited from the local community. We typically recruit from the North Central Colorado Urban Area. This 13-county Urban Area comprises the four contiguous Metropolitan Statistical Areas of north central Colorado including the Denver-Aurora-Broomfield, Fort Collins-Loveland, Boulder and Greeley.

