5. An email template used to introduce participants to the research study is also included and attached in the recruitment folder in Kuali.

B. Screening Procedures or Interview/questionnaire: Demographic information, health history (screening), and general physical activity questions will be done prior to beginning the testing session and is recorded REDCap via private survey's sent to the participant's private email. All questions asked to participants are attached in the attachment section. They are

INSTITUTIONAL REVIEW BOARD NON-EXEMPT PROTOCOL TEMPLATE

meant to provide the research staff an idea as to whether or not the participant would qualify for the study. These various forms give a better picture of the participants unique symptoms and their mobility status to be sure that participation is safe for them as well as make associations between collected data and reported status. An important confounder to consider when walking is cognitive status. The BDI and MOCA will provide additional information about cognitive and emotional status that will allow us to have a better full picture of the participant when analyzing their data. Only trained graduate students will be allowed to perform screening and determine eligibility. Additionally, if the graduate student is unsure due of eligibility due to symptom characteristics, the PI, [name], will be contacted to confirm. The Pi, [name] will review inclusion and exclusion criteria of participants weekly to confirm eligibility.

C. Informed consent process and timing of obtaining of consent

- 1 Trained graduate students will be the only personnel allowed to deliver the informed consent. [name] will be the sole consenter for this study.
- 2 The consent process will include a written and signed document along with a trained graduate student verbally describing the consent form. The participant will initial and date each page of the consent form, along with signing the last page. The trained graduate student will describe the study in lay terms in person and the participant will be allowed to ask questions. The consent process will be before any of the study procedures to confirm the participant is completely informed and consented to all portions of the study before enrolled.

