manufacturers of TENS units universally warn individuals with pacemakers, epilepsy, or are pregnant that these conditions are contraindications to use as they can lead to potential complications. We are only placing TENS on the legs, so these warnings will not be relevant to this study.

2. Psychological risk: Yes.
 - i. Breach of confidentiality: Although robust protocols and procedures are in place to keep your Protected Health Information private and secure, there is a chance of a breach of confidentiality.
 - ii. Emotional distress. Some of the questions asked may be personal or embarrassing. Participants may refuse to answer any potentially uncomfortable question. Also, participants may learn information about their balance and walking that could be potentially upsetting.
3. Social risk: No
4. Economic risk: No
5. Potential benefit of participating in the study
 - a. None
 - b. This study will further elucidate differences in neurological activity and the potential of TENS to be a rehabilitation strategy for PwMS.
 - c. The results of this study will help determine the connections between walking asymmetry and brain activity, and the potential of TENS which will be helpful when working with diseased populations.

I. Location where study will be performed: All portions of the study will be performed in the Sensorimotor Neuroimaging Laboratory at Colorado State University.

J. Collaboration (with another institution, if applicable): N/A

K. Single IRB Review for a Multi-site study (if applicable): N/A

L. Community-Based Participatory Research (if applicable): N/A

M. Personnel who will conduct the study, including:

1. Primary responsibility for the following activities, for example:
 - a. Determining eligibility: [name]
 - b. Obtaining informed consent: [name]
 - c. Maintaining participant's research records: [name]
 - d. Drawing / collecting laboratory specimens: [name]
 - e. Performing / conducting tests, procedures, interventions, questionnaires: [name]

N. Assessment of Subject Safety and Development of a Data and Safety Monitoring Plan

1. Please note that any study proposal with more than minimal risk must include a data and safety monitoring plan. Elements of the plan should include the following:

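### The protocol sets aside a pacemaker contraindication it calls universal, and no eligibility criterion excludes people with pacemakers, although every participant is scheduled for TENS

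*Combined protocol and SAP*

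**What the plan says.** Section III.H.1.iv says that "manufacturers of TENS units universally warn individuals with pacemakers, epilepsy, or are pregnant that these conditions are contraindications to use" because of potential complications. The next sentence withdraws the point: "We are only placing TENS on the legs, so these warnings will not be relevant to this study".

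Section III.D.2 (TENS Protocol) names the device and describes it as FDA-approved. It quotes no labelling on leg placement in people with a pacemaker.

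Under II.A, both sequences receive stimulation. For one, "The first group will complete split-belt treadmill training with TENS OFF during the first visit and TENS ON during the second visit"; the other has the reverse order.

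The wording in II.C that comes nearest to the three contraindications is:

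- **Pregnancy:** current pregnancy is an exclusion for all participants.
- **Epilepsy:** "MS participants must not have other neurologic conditions besides MS". This covers the MS group. For controls, the plan relies on the word neurotypical in the first inclusion criterion, which it does not define.
- **Pacemaker:** no criterion names one. The closest general phrase is "concurrent conditions affecting ability to comply with the study procedures including musculoskeletal injury", which belongs to a bullet for MS participants only.

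Section III.B describes a health-history screen before testing. The forms are "meant to provide the research staff an idea as to whether or not the participant would qualify for the study" and have a stated safety purpose. Graduate students do the screening, refer doubts about symptoms to the principal investigator, and the principal investigator checks the inclusion and exclusion criteria weekly.

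**The concern.** A protocol may depart from a manufacturer's contraindication if it shows why that is safe in its setting. This one calls the warning universal and then sets it aside on electrode site alone, with no source and no medical opinion. The eligibility list does not compensate, so a person with a pacemaker can meet every written criterion and be scheduled for stimulation.

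Participant safety is at stake; power, type I error and the analysis are not affected. The protocol rates the study as greater than minimal risk (III.H), and its list of potential benefits of taking part opens with none (III.H.5). It therefore claims no personal benefit that would offset an undocumented departure from a contraindication. The eligible age range runs to 85 or 86 years, depending on the bullet, so older adults are included.

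**Working it through.** The plan gives no figure to reproduce. The check is a count of the written rules and a comparison of sections.

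**1. Criteria listed (II.C.1 and II.C.2).** 9 inclusion + 13 exclusion = 22. Of these, 2 inclusion and 4 exclusion criteria are worded for MS participants only: 2 + 4 = 6. That leaves 22 − 6 = 16 without that restriction.

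**2. Each contraindication named in III.H.1.iv against those 22 criteria.**

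| Condition | MS participants | Controls |
|---|---|---|
| Pregnancy | excluded | excluded |
| Epilepsy | excluded, as another neurologic condition | only through the undefined term neurotypical |
| Pacemaker | no criterion | no criterion |

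Criteria that exclude a pacemaker: 0 of 22. The compliance phrase in the MS bullet is not a substitute. It concerns ability to carry out the procedures, it does not reach controls, and a protocol that declares the warning irrelevant gives little reason to apply it to a pacemaker.

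**3. Who is scheduled for TENS.** Each sequence has one TENS ON visit with a 10-minute stimulated adaptation period. By II.A, 30 + 20 = 50 of 50 participants. By the TENS Protocol in III.D.2, 30 + 30 = 60 of 60. Either way, everyone.

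**4. Later rules that might stop exposure.**

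- The withdrawal criterion (II.C.3) applies when "the researcher determines that they do not have enough mobility to complete the split-belt treadmill training paradigm". It concerns mobility.
- The safety triggers (III.N.1.e) concern unsafe walking, stumbling, tripping and falls.
- Adverse-event review (III.N.1.b) and the physician's involvement (III.N.2 and III.N.3) follow an event.

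The first two would not identify a pacemaker. The third acts only after exposure.

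**5. Screening (III.B).** The forms may well ask about pacemakers. A disclosed pacemaker would still match no exclusion, and the weekly check is made against the same list. The only stated route for doubtful cases is triggered by symptom characteristics.

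**6. Dose.** Training amplitude is 2 mA below motor threshold. To find that threshold, amplitude is raised on each muscle until contractions are seen or felt, so set-up briefly reaches motor threshold.

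**The case against.** The defence has several fair points.

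- **Pregnancy is excluded for everyone.** So the waiver did not remove every condition it names from the criteria. This stands, and it narrows the gap to the pacemaker, with epilepsy in controls a minor wording matter. The reason for the pregnancy criterion is not stated.
- **The risk section is not a screening instruction.** It is a risk statement for the ethics board. Screening is described in III.B, has a safety purpose, and uses forms that are not in the documents. This stands in part: it cannot be shown that a person with a pacemaker would pass unnoticed. It does not supply an exclusion rule.
- **A reason is given, and the whole document is light on citations.** True. But the stimulation settings, for which the plan cites only recent evidence in general terms, do not contradict a warning the plan itself calls universal. This waiver does, and so needs more support.
- **There is medical cover.** An in-house physician attends after an adverse event. This is a real safeguard, but it does not prevent exposure.
- **The hazard may be small.** Leg placement, brief stimulation, a device described as FDA-approved and a sub-threshold training amplitude may all limit it. That cannot be confirmed or refuted from the documents.

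**Conclusion.** The concern holds. Of the three contraindications the protocol reports, the pacemaker is the only one with no written exclusion in either group: 0 of 22 criteria, with all 50 participants (60 by the TENS Protocol) scheduled for one TENS ON period. The waiver rests on electrode site alone.

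These counts show who would be stimulated under the written rules, not who would be harmed. The documents give no pacemaker prevalence, so the number affected is not estimated and could be zero. The conclusion assumes only that the listed criteria govern eligibility and that no unseen form or attachment adds an exclusion. It makes no claim that leg-only TENS is dangerous with a pacemaker. The change should be made because the gap in the text is clear and closing it is cheap.

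**What to change.** - In III.H.1.iv, delete the statement that the warnings do not matter for this study.
- In II.C.2, add *implanted pacemaker* as an exclusion for all participants.
- In the same list, state that epilepsy is excluded for controls as well as MS participants.
- Check both conditions through the health-history screen already described in III.B.

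Alternatively, if the labelling of the named device expressly permits leg use in these people, keep the position but cite that labelling and a medical review in the risk section.

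The cost is a short amendment with matching screening wording and possibly the loss of a few otherwise eligible people. No new procedure is needed, because health history is already taken before testing, and the analysis is unchanged.
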